1.2.5. Drug Development and Study Rationale

The effects of tofacitinib on cytokines (including the cross over to JAK1 which may result in some attenuation of signaling by additional cytokines, such as IL-6 and IFN- γ) that are integral to lymphocyte activation, proliferation, and function and inhibition of their signaling may thus result in suppression of multiple aspects of the immune response. Cytokines IL-17, IL-21 and IL-23 have been implicated in AS pathology and antibodies to IL-17 have demonstrated efficacy in AS.³ This forms the basis of the rationale to investigate the effect of tofacitinib in active AS.

Ankylosing Spondylitis as a chronic inflammatory disease shares many characteristics with RA and PsA such as inflammation and bone erosions. The axial inflammation that is specific to AS, is the inflammation in the spine. This can lead to bone erosions, new bone formation and ankylosis of the spine. In addition, RA, PsA, and AS share many similar circulating pro inflammatory cytokines, including IL-6, IL-17, IL-23, TNF- α and TNF- γ .⁴⁵ Increased concentrations of IL-6 have been observed in patients with chronic inflammatory conditions such AS.⁴⁵⁻⁴⁸

Phase 2 study A3921119 assessed the safety and efficacy of tofacitinib in subjects with active AS at 2 mg BID, 5 mg BID and 10 mg BID. Approximately 200 subjects (~50 per arm) were randomized in a 1:1:1:1 ratio to one of 4 treatment sequences for a total of 12 weeks of treatment. At Week 12 the primary endpoint E_{\max} model ASAS20 response rates for the tofacitinib 2 mg BID, 5 mg BID and 10 mg BID treatment groups and placebo treatment group were 56.0%, 63.0%, 67.4% and 40.1%, respectively. The tofacitinib 5 mg and 10 mg BID treatment groups had numerically greater ASAS20 response rates than the placebo treated group at Week 12, and greater mean improvement from Baseline in Patient Global Assessment (PGA) of disease score, total back pain, inflammation score, and nocturnal spinal pain than the placebo group. There was statistically significant greater improvement in ASAS40 rates, ASDAS_{CRP} values, ASDAS_{CRP} clinically important improvement, improvement in mean BASDAI values, and BASDAI50 response rate at Week 12 for all tofacitinib treatment groups compared to the placebo.

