7.2.3. High Sensitivity C-Reactive Protein (hsCRP)

Blood samples will be collected at each visit for analysis of hsCRP using an assay analyzed by the central laboratory. The investigator, study site personnel and Sponsor study team will be kept blinded to the results of this test at all visits except the Screening visit.

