2 (21 September 2018)	1 (06 September 2018)	Revision to align with study protocol amendment 1 which was revised based on regulatory input on Type I error controlled secondary endpoints and mandate to follow up subjects after discontinuation of investigational products.	
 1. Updated Section 2.1 to have study objectives aligned with protocol's study objectives. 2. Updated the study schematic and clarified the investigators, subjects and sponsor will remain blinded to the first 16 weeks of treatment through the entire duration of the trial until database release in Section 2.2. 3. Updated ASAS40 at Week 16 as key secondary endpoint, re-ordered the other secondary endpoints to have same order of hierarchy in Type I error controlled hypothesis testing in Section 3.2. 4. Clarified the derivation of prior treatment history as a randomization factor in Section 3.4.1. 5. Added prior exposure to non-TNFi bDMARD as a protocol deviation for exclusion from Per

			
Protocol Analysis Set in Section 4.2.2.
 
 6. Updated the terminology of “study treatment” to “investigational product” to be consistent with protocol in Section 4.2.3. 7. Removed the statements regarding EMA’s consideration of ASAS40 as primary endpoint in Section 5.1. 8. For global type I error controlled endpoints in Section 5.1, changed SF-36v2 Physical Functioning domain to Physical Component Summary and added ASQoL to the hierarchy of testing. Also clarified the step-down testing procedure. 9. Added descriptions of analyses of ASAS20 at Week 16 for subjects who discontinued investigational product or study early in Section 6.1.2. 10. Clarified/Added EQ-5D-3L Utility Score (UK) to the list of endpoints in Sections 3.2.2, 6.3 and 9.8 (Table 8) as an endpoint, provided method of its derivation in Section 9.2.8 and data range in Section 9.5.
--	--	--	---

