3.2.2. Other Secondary Endpoints

- ASAS20 response at all other time points (Weeks 2, 4, 8, 12, 24, 32, 40, and 48) (see [Section 9.2.1](#));
- ASAS40 response at all other time points (Weeks 2, 4, 8, 12, 24, 32, 40, and 48) (see [Section 9.2.1](#));
- Change from Baseline (Δ) in Ankylosing Spondylitis Disease Activity Score using C-Reactive Protein (Δ ASDAS_{CRP}) at all time points (Weeks 2, 4, 8, 12, 16, 24, 32, 40, and 48) (see [Section 9.2.4](#));
- Δ in High Sensitivity C-Reactive Protein (Δ hsCRP, mg/L) at all time points (Weeks 2, 4, 8, 12, 16, 24, 32, 40, and 48);
- Δ in Ankylosing Spondylitis Quality of Life (Δ ASQoL) at Weeks 16 & 48;

A total score is calculated by summing the 18 items. The total score ranges from 0 to 18, with higher values indicating more impaired health-related quality of life.

- Δ in 36-Item Short Form Health Survey Version 2 (Δ SF-36v2), Acute at Weeks 16 & 48;

This survey yields 10 endpoints: 8 general health domains: physical functioning, role limitations due to physical health, bodily pain, general health perceptions, vitality, social functioning, role limitations due to emotional problems, and mental health. These domains can also be summarized as physical and mental component summary scores (see [Section 9.2.7](#)).

- Δ in Bath Ankylosing Spondylitis Metrology Index (Δ BASMI) and its 5 components (Δ in Lateral Spinal Flexion, Tragus-to-Wall Distance, Lumbar Flexion [as measured by Modified Schober's test score], Maximal Intermalleolar Distance, and Cervical Rotation) at all time points (Weeks 2, 4, 8, 12, 16, 24, 32, 40, and 48) (see [Section 9.2.3](#));
- Δ in Functional Assessment of Chronic Illness Therapy-Fatigue (Δ FACIT-F) (Total Score, Experience Domain Score, and Impact Domain Score) at all time points (Weeks 2, 4, 8, 12, 16, 24, 32, 40, and 48);

This instrument has 13 items that assess fatigue. Instrument scoring yields a range from 0 to 52 for Total Score, with higher scores representing better subject status (less fatigue). For Experience Domain Score, range is 0-20; for Impact Domain Score, range is 0-32 (see [Section 9.2.9](#)).

- Δ in Patient Global Assessment of Disease (Δ PGA) at all time points (Weeks 2, 4, 8, 12, 16, 24, 32, 40, and 48). PGA is one of the 4 ASAS20/ASAS40 components;

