Global Type I Error Control (for the primary endpoint and a select set of secondary endpoints): The family-wise Type I error rate will be controlled at the 2-sided 5% (or equivalently 1-sided 2.5%) significance level using a step-down testing procedure for the primary endpoint of ASAS20 at Week 16, the key secondary endpoint of ASAS40 at Week 16, and a select set of secondary endpoints at Week 16 tested in the sequence below: ASAS20, ASAS40, Δ ASDAS_{CRP}, Δ hsCRP, Δ ASQoL, Δ SF-36v2 Physical Component Summary (PCS), Δ BASMI, and Δ FACIT-F Total Score. When an endpoint fails to declare statistical significance, this endpoint and the remaining endpoints lower in the hierarchy will be considered non-significant. The rationale for the selection and ordering of the select set of secondary endpoints are clinical importance, precedence and likelihood of statistical success based on the results of the A3921119 study.

Type I Error Control for Endpoints in the ASAS Family: Δ PGA, Δ in total back pain, Δ BASFI, and Δ in inflammation (average of questions 5 and 6 of BASDAI) are the 4 ASAS components used in deriving ASAS20, thus they are considered belonging to the ASAS family of endpoints. A step-down testing procedure will be applied to them and tested in the sequence below: ASAS20, Δ PGA, Δ in total back pain, Δ BASFI, and Δ in inflammation (average of questions 5 and 6 of BASDAI) at Week 16. When an endpoint fails to declare

statistical significance, this endpoint and the remaining endpoints lower in the hierarchy will be considered non-significant. Though this testing scheme does not protect the Type I error for the family of all possible comparisons, it will provide Type I error protection for testing the family of ASAS endpoints.

Type I Error Control for ASAS20 at Earlier Time Points: In order to be more rigorous about establishing the onset of efficacy as measured by ASAS20 at the earliest time point at which there is statistical separation between tofacitinib 5 mg BID and placebo, a step-down approach with the ASAS20 from Week 16 to earlier time points (order of testing: Weeks 16, 12, 8, 4, and 2) will also be used for each time point. Though this testing scheme does not protect the Type I error for the family of all possible comparisons, it will provide Type I error protection for testing the family of ASAS20 time points.

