5.2.2. Analyses for Continuous (Repeated) Data

Repeated measures data for continuous or order-categorical (analyzed as continuous) endpoints will be analyzed as change from baseline as appropriate with a mixed model for repeated measures (MMRM) that includes fixed effects of treatment group, visit, treatment-group by visit interaction, stratification factor (ie, prior treatment history: "bDMARD-naïve" vs "TNFi-IR or bDMARD Use [Non-IR]") at randomization, stratification-factor by visit interaction, baseline value, and baseline-value by visit interaction. A common unstructured variance-covariance matrix will be used, provided the model converges, otherwise an alternative covariance structure, eg, heterogeneous compound symmetry (CSH), will be attempted. The Kenward-Roger degrees of freedom approximation will be used. This model is referred to as MMRM. Comparison of tofacitinib 5 mg BID to placebo (providing least squares means [LSM] of the treatments, LSM of the treatment difference, 2-sided p-value and 95% CI) at each time point during the first 16 weeks will be generated using this MMRM. Comparisons of tofacitinib 5 mg BID and placebo → tofacitinib 5 mg BID for visits after Week 16 through Week 48 are also reported from the same model. For each endpoint, the number of subjects by treatment group in the FAS, the number of subjects by treatment group included in the MMRM and the number of subjects by treatment group evaluable at each of the visits are also to be reported. If the Baseline is missing or if there are no post-baseline measurements, the subject will be excluded from this analysis (see [Section 4.1](#)).

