When using the on-drug data, the treatment comparisons of these binary endpoints correspond to Estimand 1 ([Section 2.1.1](#)). Only ASAS20 and ASAS40 (the only two binary endpoints under Type I Error Control at earlier time points) will be repeated using the on-study data ([Section 9.1](#)), and the treatment comparisons of these two binary endpoints correspond to Estimand 2 ([Section 2.1.1](#)).

MMRM without imputation for missing data described in [Section 5.2.2](#) will be used to analyze the change from Baseline for the following endpoints. The model will include up to Week 16 (Weeks 2, 4, 8, 12, and 16) for the Week 16 analysis while all the time points of the entire study duration (Weeks 2, 4, 8, 12, 16, 24, 32, 40, and 48) for the Week 48 analysis as indicated below for each of the endpoints. Prior treatment history will be derived from the clinical database and used in the analysis (see [Section 3.4.1](#) and [Section 9.11](#)). When the on-drug data is used ([Section 9.1](#)), the treatment comparisons of these endpoints correspond to Estimand 4 ([Section 2.1.2](#)) for both Week 16 and Week 48 analyses. These same analyses will be repeated only for the following Type I error controlled secondary endpoints: Δ ASDAS_{CRP}, Δ hsCRP, Δ BASMI (as well as the 5 non-Type I error controlled components), Δ FACIT-F (Total score as well as the non-Type I error controlled endpoints of Experience Domain and Impact Domain Scores), Δ PGA, Δ in Total Back Pain, Δ BASFI and Δ Inflammation (supportive) ([Section 6.1.2](#)) using the on-study data ([Section 9.1](#)) for the Week 16 analysis only, and the treatment comparisons of these endpoints correspond to the Estimand 5 ([Section 2.1.2](#)).

- Δ ASDAS_{CRP} at all time points (Weeks 2, 4, 8, 12, 16, 24, 32, 40, and 48);

- Δ hsCRP (mg/L) at all time points (Weeks 2, 4, 8, 12, 16, 24, 32, 40, and 48);
- Δ BASDAI at all time points (Weeks 2, 4, 8, 12, 16, 24, 32, 40, and 48);
- Δ BASMI and its 5 components (Δ in Lateral Spinal Flexion, Tragus-to-Wall Distance, Lumbar Flexion [as measured by Modified Schober's test score], Maximal Intermalleolar Distance, and Cervical Rotation) at all time points (Weeks 2, 4, 8, 12, 16, 24, 32, 40, and 48);
- Δ BASFI at all time points (Weeks 2, 4, 8, 12, 16, 24, 32, 40, and 48);
- Δ MASES at all time points (Weeks 4, 8, 12, 16, 24, 32, 40, and 48);
- Δ SJC(44) at all time points (Weeks 2, 4, 8, 12, 16, 24, 32, 40, and 48);

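### Should the change in hsCRP, fourth of eight tests in the global sequence, be tested on a log scale rather than in mg/L?

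*SAP*

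**What the plan says.** SAP 3.2.2 defines the endpoint as the change in "hsCRP, mg/L) at all time points (Weeks 2, 4, 8, 12, 16, 24, 32, 40, and 48", and SAP 6.3 carries the same unit into the analysis, listing the change in "hsCRP (mg/L) at all time points (Weeks 2, 4, 8, 12, 16, 24, 32, 40, and 48". SAP 5.2.2 gives one repeated-measures model for all such endpoints. Its fixed effects are treatment, visit, their interaction, and "stratification-factor by visit interaction, baseline value, and baseline-value by visit interaction". No transformation is named for hsCRP, and the only repeat analysis uses on-study instead of on-drug data.

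The global sequence in SAP 5.1 is ASAS20, ASAS40, ASDAS-CRP, hsCRP, ASQoL, SF-36v2 PCS, BASMI, FACIT-F Total. The stopping rule is strict: "When an endpoint fails to declare statistical significance, this endpoint and the remaining endpoints lower in the hierarchy will be considered non-significant". The order is said to reflect, among other things, "likelihood of statistical success based on the results of the A3921119 study". No Phase 2 hsCRP figures are given.

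Two further points bear on the scale. SAP 9.2.4 already uses the natural log of hsCRP plus 1 inside ASDAS-CRP, the test just before hsCRP, and sets hsCRP to 0.199 mg/L with reference to the assay limit of 0.2 mg/L. Protocol 7.2.3 says the "Sponsor study team will be kept blinded to the results of this test at all visits except the Screening visit".

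**The concern.** A mean change in mg/L is sensitive to a few very high values. If hsCRP has a heavy upper tail and the drug lowers it by a modest, roughly constant percentage, the mg/L test gives away power that a log-scale test would keep. In most positions that would cost one secondary result. Here four endpoints stand behind it, including quality of life and fatigue, and none can be claimed if hsCRP misses, whatever their own p-values.

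The remedy also looks cheap. Screening hsCRP is open to the sponsor, so its spread can be examined without unblinding. Protocol 9 lets the SAP modify analyses other than the primary without a protocol amendment. The SAP gives no reason for choosing mg/L.

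**Working it through.** **The plan's own figure.** The only stated power is for ASAS20: 40% vs 60%, 120 per arm, two-sided 5%. SE = √(0.4×0.6/120 + 0.6×0.4/120) = 0.0632. Then 0.20/0.0632 − 1.960 = 1.20, which gives 88.5% against the stated 89%. Nothing comparable is stated for hsCRP, so everything below rests on assumptions.

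**Model.** From the documents: 120 per arm, two-sided 5%, baseline as covariate, values below 0.2 set to 0.199. The Week 16 change f(post) − f(base) is regressed on treatment and f(base), with f either the identity or ln(x+1). Because the SAP model crosses its covariates with visit, this matches the Week 16 estimate of the unstructured model when data are complete. The stratum term is left out.

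**Case A: log-normal hsCRP, proportional effect in everyone** (assumed median 8 mg/L, correlation 0.6). Power, mg/L vs log:

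| Reduction | log SD 0.7 | 0.9 | 1.1 | 1.3 |
|---|---|---|---|---|
| 20% | 73 vs 87% | 46 vs 66% | 28 vs 49% | 17 vs 37% |
| 30% | 98 vs 99.8% | 83 vs 97% | 58 vs 87% | 38 vs 75% |
| 40% | 100 vs 100% | 98 vs 100% | 86 vs 99% | 65 vs 96% |

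At a 60% reduction both scales reach at least 96%. The widest gap found at a 30% reduction is 52 vs 94% (log SD 1.3, correlation 0.8). With no effect, rejection at log SD 0.9/1.1/1.3 is 5.4/4.7/3.9% in mg/L and 5.1/4.8/4.4% on the log scale, so both tests are valid.

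The consequence for a claim is the chance of passing ASDAS-CRP, hsCRP and ASQoL in turn, with ASQoL's own power assumed to be 90%. At a 30% reduction and log SD 0.7/0.9/1.1/1.3 it is 88 vs 89, 76 vs 88, 53 vs 78 and 34 vs 67%. At a 60% reduction the scales differ by at most 3 points.

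**Case B: same model, different tail** (assumed median 10, correlation 0.6, proportional effect in everyone). Let the log SD be 1.6 below the median and 0.5 above. The overall log variance is (1.6² + 0.5²)/2 − [(1.6 − 0.5)/√(2π)]² = 1.405 − 0.193 = 1.212, an SD of 1.10 (about 1.08 after the floor at 0.199). By log SD alone this cannot be told from the 1.1 column of Case A.

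| Log SD below / above median | 20% reduction | 30% reduction |
|---|---|---|
| 1.6 / 0.5 | 80 vs 58% | 99 vs 92% |
| 1.5 / 0.6 | 70 vs 56% | 98 vs 92% |

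At 1.3 / 0.8 and a 30% reduction the log scale is slightly ahead again, 89 vs 92%.

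**Case C: log-normal as in Case A, but only subjects above 20 mg/L respond, with a 50% reduction.** At log SD 0.9/1.1/1.3 and correlation 0.6: 28 vs 23, 28 vs 24 and 26 vs 26%. At correlation 0.8: 55 vs 35, 60 vs 40 and 55 vs 42%.

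**Can the cases be told apart beforehand?**
- *Screening hsCRP.* With 240 subjects a log SD of 1.1 has a 95% interval of about 1.01 to 1.21 (chi-square, 239 df). The spread would be well known, but Cases A and B share it. Screening values can show tail shape but not who responds.
- *Phase 2.* Protocol 1.2.5 describes that trial as "Approximately 200 subjects (~50 per arm) were randomized in a 1:1:1:1 ratio". At log SD 1.1 and correlation 0.6, SE = 1.1 × √(1 − 0.6²) × √(2/50) = 0.176. An observed 30% reduction is ln 0.70 = −0.357, and −0.357 ± 1.96 × 0.176 runs from −0.702 to −0.012, a reduction between 1% and 50%. Under Case A, P(hsCRP > 20) = P(Z > ln(20/8)/1.1 = 0.83) = 0.20, about 10 subjects per arm. That is too few to show whether response is confined to them.

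**The case for a change.** The best argument for a change is that the check is blinded, cheap and consistent with this SAP, which already logs hsCRP one test earlier. Choosing a scale from pooled pre-treatment values and an earlier trial uses no treatment difference from this one, so Type I error is safe. If the upper tail is heavy and the effect modest, the gain is large: about 30 points at log SD 1.1 and a 30% reduction. The SAP also states no reason for mg/L.

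The Case A arithmetic stands, and so does the missing rationale. What does not stand is the step from there to a better plan. A rule that moves to the log scale when the log SD of Screening hsCRP is high would pick the weaker test in Case B. Lower-tail shape is a live question: entry sets no minimum hsCRP, and Protocol 3 lets the sponsor limit subjects below 0.287 mg/dL (2.87 mg/L), which alters that tail. The Phase 2 check meant to rule out Case C is too coarse for the task.

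The switch also has costs. The estimand would move from a mean difference in mg/L to roughly a ratio of geometric means of hsCRP plus 1. The fourth test would overlap more with ASDAS-CRP, which already contains log hsCRP. The SAP version history says the controlled set was "revised based on regulatory input on Type I error controlled secondary endpoints", so a new scale might have to be discussed again. It would have to be dated before the Week 16 unblinding, and the documents do not show that this was still possible. The venous thromboembolism check added for all remaining visits by Amendment 3 is scheduled only from Week 32, which suggests that subjects were then well past Week 16.

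**Conclusion.** No change to the plan. The mg/L change is used consistently, it is a legitimate estimand, and its test keeps its level. The scale affects efficiency at one step of the sequence. It does not affect ASAS20, ASAS40, ASDAS-CRP, or the three separate families (ASAS components, earlier ASAS20 and earlier ASAS40 time points).

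The difference in power runs from about 40 points in favour of the log scale (log-normal, wide spread, 30% proportional reduction) through nil (narrow spread or a reduction of 60% or more) to about 20 points in favour of mg/L (long lower tail, or response only at high baseline). All of these rest on assumed distributions and effects, because the documents supply none, so the loss or gain in this trial cannot be determined from them. The sponsor held the Phase 2 results when setting the order. Their absence from the SAP does not show that they were ignored.

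A supplementary log-scale analysis or a sentence giving the reason for mg/L would do no harm, but neither would alter a controlled result. Keeping mg/L is a fair trade-off.

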6.4. Subset (Subgroup) Analyses

6.4.1. Subgroup Analyses for Primary Endpoint of ASAS20 at Week 16

All subgroup comparisons for the primary endpoint ASAS20 at Week 16 will be made on the FAS with missing value handled by MR=NR using the on-drug data corresponding to Estimand 1 for the following comparison only:

- Tofacitinib 5 mg BID vs. Placebo.

Subgroup analysis will be performed for each of the following subgroup variables and their categories in parentheses:

- Prior treatment history - 2 categories ("bDMARD-naïve", "TNFi-IR or bDMARD Use [Non-IR]") where prior treatment history is derived from the clinical database (see [Appendix Section 9.11](#));
- Prior treatment history – 3 categories ("bDMARD-naïve", "TNFi-IR", "bDMARD Use [Non-IR]") where prior treatment history – 3 categories is derived from the clinical database. Subjects under "bDMARD Use (Non-IR)" category are not TNFi-IR and have prior bDMARD Use without IR. This subgroup analysis is only done when there is sufficient number of subjects in the "bDMARD Use (Non-IR)" category (see [Appendix Section 9.11](#));
- Geographic region – 4 regions ("North America (US and Canada)" [United States, Canada], "European Union" [Bulgaria, Czech Republic, France, Hungary, Poland], "Rest of World" [Ukraine, Russia, Australia, Turkey], "Asia" [China, South Korea]);
- Gender (Female, Male);
- Race (White, Asian, Other), when a subject selects more than one race category, this subject will be grouped to the "Other";
- Age at Baseline (<65, \geq 65 years);
- Baseline weight (<60, \geq 60 to \leq 100, >100 kg);

- Baseline Body Mass Index (BMI) (<25, ≥25 to <30, ≥30 to <40, and ≥40 kg/m²);
- AS disease symptom duration (<5, ≥5 years);
- Baseline AS disease activity (ASDAS_{CRP} <1.3 [inactive disease], ≥1.3 to <2.1 [low disease activity], ≥2.1 to ≤3.5 [high disease activity], > 3.5 [very high disease activity] units, and continuous) (van der Heijde et al. 2016; Machodo et al., 2018);⁹
- Baseline hsCRP (≤2.87, >2.87 mg/L), where 2.87 mg/L (the upper limit of normal) is defined in this study as elevated;
- Baseline smoking status (Never Smoked, Former Smoker, Current Smoker);
- Day 1 Concomitant csDMARD Use (Yes, No);
- HLA-B27 (Positive, Negative).

Estimates of the treatment difference between tofacitinib 5 mg BID and placebo at Week 16 along with the 95% CI without p-value, will be presented for each category of a subgroup variable. The normal approximation using CMH approach adjusting for prior treatment history ("bDMARD-naïve" vs. "TNFi-IR or bDMARD Use [Non-IR]") (see [Sections 3.4.1](#) and [5.2.1.1](#) as well as [Section 9.11](#)) will be used for each category of a subgroup variable, except for the subgroup of prior treatment history.

In addition to Week 16, subgroup analysis of ASAS20 by prior treatment history (2 category definition: "bDMARD-naïve", "TNFi-IR or bDMARD Use [Non-IR]") and (3-category definition: "bDMARD-naïve", "TNFi-IR", and "bDMARD Use [Non-IR]" provided there is sufficient number of subjects in the category of bDMARD Use [Non-IR]) will be conducted at each visit prior to Week 16. ASAS20 will be analyzed separately by prior treatment history (both 2-category and 3-category definitions) using the normal approximation approach to the difference in binomial proportions on the FAS ([Section 4.1](#)) with missing value considered as non-responsive (ie, MR=NR). For each category of "bDMARD-naïve" and "TNFi-IR or bDMARD Use (Non-IR)" of the 2-category definition, as an example, the 95% CI of the treatment difference is calculated as:

$$(\hat{p}_A - \hat{p}_B) \pm z_{0.975} \sqrt{\frac{\hat{p}_A(1 - \hat{p}_A)}{n_A} + \frac{\hat{p}_B(1 - \hat{p}_B)}{n_B}}$$

where \hat{p}_A and \hat{p}_B represent the estimated response rates for tofacitinib 5 mg BID and placebo respectively, and n_A and n_B are their respective sample sizes. $z_{0.975}$ is the 97.5th percentile of the standard normal distribution. No p-value will be produced. The method of handling 0 or 100% response rate in either or both treatment groups can be found in [Section 5.2.1.1](#).

The primary purpose of subgroup analyses is to check for consistency of the primary endpoint results across subgroup categories, ie, making sure overall results are not driven by some subset of subjects (ie, particular categories of a subgroup). Graphical display (eg, forest plots) of the treatment differences in ASAS20 at Week 16 between tofacitinib 5 mg BID and placebo will be presented. There is no intention to have any specific inference within subgroup variables, therefore only 95% CI's are produced without corresponding p-values.

6.4.2. Subgroup Analyses for Key Secondary Endpoint of ASAS40 at Week 16

As ASAS40 at Week 16 is the key secondary endpoint, all of the subgroup analyses described for ASAS20 in [Section 6.4.1](#) will also be performed on ASAS40 at Week 16. The analysis by prior treatment history described for ASAS20 in [Section 6.4.1](#) will also be performed on ASAS40. Only the on-drug data corresponding to Estimand 1 will be used (see [Appendix Section 9.1](#)). The other Type 1 controlled secondary endpoints will not be included in subgroup analyses.

